## **D. Data, Study Sample, Outcomes, and Other Variables**

### **D.1. Data and Study Samples**

The study sample will be recruited from the population of eligible households in Monroe, Onondaga, and Westchester counties, New York. We will randomly select 50 households per county into the treatment arm, and 100 households per county into the control arm.

Data will be obtained from two sources:

1) A web-based survey for all study participants at baseline, at 6 months after treatment begins, at 12 months after treatment begins, and at 18 months after treatment begins (6 months after treatment ends). This survey will collect information on caretaker and child demographic, health, behavioral, educational, and social characteristics. All variables will be collected at baseline. We will repeat data collection for all time-varying variables at each post-baseline wave of the survey.

2) OCFS administrative records linked to the study participants and their children using the DOB and name of the study participant and all minor children in the participant's household. Data will be provided by OCFS as family-specific and child-specific counts of a series of events related to child maltreatment reports and agency interventions.

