## Secondary outcomes:

Secondary outcomes are related to child and family health, well-being, and stability. All outcomes are measured during each wave of survey data collection [baseline, 6 months, 12 months, 18 months]. For all measures derived from additive indices, we will treat measures as continuous. If the empirical distributions of additive indices are roughly symmetric, we will treat them as continuous real numbers. If the empirical distributions of additive indices are skewed, we will treat them as non-negative integers.

- Parental self-reported general health (19 physical health items derived from SF-36): items scored following RAND Corporation SF-36 scoring instructions for included questions. Additive index
- Mental health (Kessler 10 plus) Each item is scored from one 'none of the time' to five 'all of the time'. Scores of the 10 items are then summed, yielding a minimum score of 10 and a maximum score of 50. Additive index
- Stress and coping (Perceived Stress Scale - 4): Each item is scored from "never" to "all of the time" on a 5-point scale. Scores of 4 items are then summed, yielding a minimum score of 0 and a highest score of 16. Higher scores are correlated to more stress. Additive index
- Family dynamics and parenting (CHAOS): Each item is scored "yes" or "no". Scores of the items are then summed. The higher the score the higher the level of environmental chaos in the home. Additive index
- Parental Stress Scale: 18-item questionnaire assessing parents' feelings about their parenting role, exploring both positive aspects (e.g. emotional benefits, personal development) and negative aspects of parenthood (e.g. demands on resources, feelings of stress). Each item is scored on a 5-point Likert scale. Parental stress scores range from 18 to 90, with lower scores indicating lower levels of parental stress. Additive index
- Food insecurity: In the past four weeks, did you worry that your household would not have enough food? Binary
- Adult Hope Scale: 12 items scored on an 8-point ordinal scale. Additive index
- Child missed medical care: Parental yes/no report of any child in home with missed medical care in preceding 6 months. Binary
- Child truancy: Parental report of day of missed school for each child in the home aged 6-17 in the preceding 6 months. Ordinal [no missed days; 1-3 days; 4-6 days; 7-10 days; 11 or more days; child not enrolled in school]

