- Hours per week of relative childcare: Parent-reported number of hours each week each child 0-5 spends receiving care from a relative other than a parent or guardian.
- Hours per week of non-relative child care: Parent-reported number of hours each week each child 0-5 spends receiving care from a non-relative. Non-negative continuous
- Hours per week of formal childcare: Parent-reported number of hours each week each child 0-5 spends receiving care in a day care center, preschool, or prekindergarten. Non-negative continuous
- Financial-well being (CFPB Financial Well-Being Scale: Each item is scored 0 to 4 and summed to a total following CFPB scoring instructions. Additive index.
- Housing instability: 3-items counting number of moves, rating home quality, and rating neighborhood quality. Additive index.

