### D.3. Participant Characteristics

We will collect the following demographic and socioeconomic information from participants:

- Age
- Gender
- Self-reported race
- Self-reported ethnicity
- Number of adults in household
- Number of children in household
- Educational attainment
- Monthly income from employment
- Monthly income from other government benefits
- Employment
- Health Insurance Status (Insured versus uninsured)
- Child Health Insurance Status (If any child in home is uninsured)
- Housing status

In the event that there are high levels of missingness for any key covariate (i.e., >2%), multiple imputation methods will be used.

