### **E.2. Statistical specification**

Our primary analytic approach is an analysis based on the intent-to-treat principle that compares outcomes for those randomized into the treatment group to those who were randomized into the control group.

Our models account for time-stable heterogeneity across individuals and treatment sites using random intercepts for each individual enrolled in the study, for each time period during which surveys are collected, and for the county from which their qualifying OCFS case originated. These random effects adjust for correlation induced by repeated measurements of individuals over time, time period effects, and clustering of outcomes within counties.

Our regression models for outcome variable  $y$  take the following general form:

$$\mu = E(y|T, X) = \alpha_i + \delta_j + \gamma_k + \beta T_i + c_j T_i + \theta X_{ij}$$

$$\begin{pmatrix} \alpha \\ \delta \\ \gamma \end{pmatrix} \sim N(0, \Sigma)$$

Where  $T$  indicates selection into the treatment group,  $X$  is a matrix of demographic characteristics,  $i$  indicates an individual participant,  $k$  indicates county of residence at the time of study enrollment,  $j$  indicates survey time period,  $\alpha$  is a vector of individual-level intercepts,  $\delta$  is a vector of time period intercepts,  $\gamma$  is a vector of county-level intercepts,  $\beta$  is the time-stable component of the treatment effect,  $c$  is a vector of time-varying components of the treatment effect, and  $\theta$  is a vector of coefficients for demographic predictors.

The relationship between the treatment and outcomes of interest may vary as a function of time. We treat temporal relationships as potentially nonlinear, and model the relationship between time, treatment, and outcomes of interest using a series of time-period intercepts. We estimate a unique intercept for each treatment period as well as an interaction between treatment status and treatment period to capture time-varying effects of treatment.

For all continuous (additive index) outcomes with a roughly symmetric distribution, we treat the outcome as following a linear model where

$$y \sim N(\mu, \sigma^2)$$

For all binary outcomes, we treat the outcome as following a Bernoulli model

$$y \sim \text{Bernoulli}(p)$$

$$E(p|T, X) = \text{logit}^{-1}(\mu)$$

And for all count outcomes and additive index outcome with a non-symmetric distribution, we treat the outcome as following a negative binomial model

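### Child age should be named as a covariate for the three childcare-hours outcomes and school absence, whose age-banded children change between waves

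*Combined protocol and SAP*

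**What the plan says.** D.2 sets four secondary outcomes on age-banded children. Hours of relative, non-relative and formal care are asked about children aged 0 to 5; the formal-care item is "Parent-reported number of hours each week each child 0-5 spends receiving care in a day care center, preschool, or prekindergarten". School absence is asked "for each child in the home aged 6-17 in the preceding 6 months". On timing, D.2 says: "All outcomes are measured during each wave of survey data collection [baseline, 6 months, 12 months, 18 months". It does not say whether a child's band is fixed at baseline or applied afresh at each wave, or how siblings are combined.

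E.2 fits intercepts for participant, period and county, a treatment effect, and "an interaction between treatment status and treatment period to capture time-varying effects of treatment". The covariate term X "is a matrix of demographic characteristics", with no list of items. The only list is in D.3. It is headed as information from participants, who are adult caregivers, and it includes "Number of children in household" but not the children's ages. D.1 says that the survey collects child as well as caretaker demographics, and that administrative records are linked "using the DOB and name of the study participant and all minor children" in the household.

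**The concern.** Questions about children of a given age, repeated at four waves, most naturally refer to whoever is in the band at that wave. Children then leave the 0-5 measures at their sixth birthday and enter the absence measure, and newborns join.

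Hours of care may vary a good deal with age. The formal-care item may also drop at age 5 for children who start kindergarten, which it does not count. Variation of this kind goes into the residual if age is not modelled. As a child grows older it also produces change within a family, which a participant intercept cannot remove.

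Two things are at stake: standard errors larger than they need be, and treatment-by-period terms that do not refer to one fixed group of children. A child's age at a wave follows from the date of birth, so the cash cannot alter it and adjustment for it is safe.

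**Working it through.** **Inputs.** The bands and waves come from D.2. The arms are 3 × 50 = 150 and 3 × 100 = 300 households (C and D.1). The plan gives no age-out share, child-age distribution or distribution of hours, so there is no figure of its own to reproduce. Those inputs are assumed below.

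**Share leaving the band.** Read 0-5 as up to the sixth birthday, 72 months wide.
- Uniform ages, share = months/72: 6/72 = 8.3%, 12/72 = 16.7%, 18/72 = 25.0%.
- Linear tilt t in the age density, f(u) = 1 + t(2u − 1) with u = age/72 months. The share with u > 0.75 is 0.25 + 0.1875t: 15.6% at t = −0.5 and 34.4% at t = +0.5.
- Ages 6-17, 144 months wide: 18/144 = 12.5% leave at the top by 18 months, while children from the younger band enter at the bottom.

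**Bias and precision at one wave.** This simulation had no true effect, 150 v 300 households, one child each, and uniform baseline ages; only children still under 6 at 18 months were kept. Hours rose linearly from 0 at birth to a ceiling at age 5. Household and residual SDs were both 8, with 2,000 runs. The mean arm difference lay between −0.06 and +0.03 hours with or without age, so ageing brought no bias. Variance saved = 1 − (SE with age / SE without)².

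| Hours at age 5 | SE without age | SE with age | Variance saved |
|---|---|---|---|
| 0 (flat) | 1.294 | 1.298 | none |
| 7.5 | 1.339 | 1.324 | 2% |
| 15 | 1.348 | 1.299 | 7% |
| 30 | 1.500 | 1.279 | 27% |

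In general, omitting age inflates the SE by 1/√(1 − R²): 1.03 at R² = 0.05, 1.12 at 0.20 and 1.20 at 0.30.

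**Precision over all waves.** This simulation had 150 v 300 families, 60% of them with a child aged 0-5, and no births. Family, child and residual SDs were 9, 6 and 10. The analysis was an exchangeable GEE by family with wave × treatment, 40 runs per profile.

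| Hours at ages 0 to 5 | SE, 18-month effect | Variance saved | SE, 18-month interaction | Variance saved |
|---|---|---|---|---|
| 8, 12, 14, 16, 18, 10 | 1.95 → 1.91 | 4% | 1.87 → 1.77 | 10% |
| 6, 10, 14, 18, 22, 5 | 2.07 → 1.89 | 17% | 2.03 → 1.70 | 30% |
| 4, 8, 12, 20, 28, 2 | 2.24 → 1.87 | 30% | 2.40 → 1.73 | 48% |

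None of these profiles is flat, and all assume a drop at age 5. In a repeat with one or two children per family, a truly flat profile gave 0%. The interaction savings for the three profiles were 10%, 31% and 51%, and they fell to 2%, 5% and 15% when 5-year-olds were left out. Much of the gain on the interaction therefore comes from the assumed drop at 5.

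**Changing mix.** Suppose a constant effect of +4 hours in ages 3-4 only, uniform baseline ages and no births. The share aged 3-4 after w years is 2/(6 − w), so the average effect is 8/(6 − w): 8/5.5 = 1.45, 8/5 = 1.60 and 8/4.5 = 1.78 hours at 6, 12 and 18 months. The drift is 1.778 − 1.455 = 0.32 hours. Set against the interaction SEs of 1.70 to 2.40, that is 0.13 to 0.19 of one SE. If births replace all leavers, the drift is zero.

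**The case against.** The strongest reply is that the plan is silent rather than wrong. X is not itemised, it carries a participant-and-period subscript that would admit a time-varying covariate, and child demographics are collected. A reader might infer that child age is excluded from the model; the documents show only that it is unspecified. That the children change between waves is likewise an inference, though the natural one.

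A reader might also infer that ageing biases the effects of cash. It does not. Ageing is the same in both arms in expectation, and the period intercepts take up the common shift. Nor do the figures support a worry that the changing mix will create a false time trend: the drift shown is under a fifth of a standard error and needs an effect confined to two years of age. The precision gain is zero if hours do not vary with age. It was worked out for formal hours only, not for relative care, non-relative care or absence. All of this stands.

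Two further remedies look attractive but should not be adopted.
- **Limiting the childcare outcomes to children not yet in kindergarten** conditions on a family decision made after randomisation, which cash might influence. It also discards data. Approximated by dropping all 5-year-olds, with age adjusted, the 18-month SE was 2.12, against 1.94, 2.07 and 2.27 with the plan unchanged: worse in two of three profiles. Leaving kindergarten out of formal childcare is a choice of definition, not an error.
- **Standardising effects to the baseline age distribution** does nothing on the linear scale without treatment-by-age terms. Without births, no baseline child is under 1.5 years at 18 months, so the youngest quarter of that distribution would have no data.

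What survives is the case for naming child age. It rests on a variable that treatment cannot change and that the study already holds.

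**Conclusion.** The point holds as one of precision and interpretation on four secondary outcomes. The primary outcomes, taken from administrative records, are untouched.

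About a quarter of the baseline 0-5 group ages out by 18 months if ages are uniform. That is not an upper limit: the tilts shown give 16% to 34%. The avoidable share of the variance of the 18-month effect on formal hours runs from nothing, if hours are flat in age, to about 30%, if they vary steeply. The documents give neither an age distribution nor an hours profile, so this is a range under assumptions and not an estimate.

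The treatment-by-period terms describe a somewhat different set of children at each wave. That calls for care in wording, not for doubt about the comparison of arms within a wave.

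**What to change.** In E.2, for the three childcare-hours outcomes and school absence only, add child age at the wave, computed from date of birth, as one-year categories or a spline. If an outcome is combined to household level, use instead the number of eligible children in each age year.

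When effects at 6, 12 and 18 months are compared, note that the age mix changes. Alternatively, add a sensitivity analysis limited to children listed at baseline whose birth dates keep them in the band at all four waves. With uniform ages that keeps (72 − 18)/72 = 75% of the baseline 0-5 group and (144 − 18)/144 = 87.5% of the baseline 6-17 group. It fixes the set of children, although they still grow older between waves.

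The cost is SAP wording, one derived variable from dates of birth already collected, and a few extra model parameters.

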### D.3. Participant Characteristics

We will collect the following demographic and socioeconomic information from participants:

- Age
- Gender
- Self-reported race
- Self-reported ethnicity
- Number of adults in household
- Number of children in household
- Educational attainment
- Monthly income from employment
- Monthly income from other government benefits
- Employment
- Health Insurance Status (Insured versus uninsured)
- Child Health Insurance Status (If any child in home is uninsured)
- Housing status

In the event that there are high levels of missingness for any key covariate (i.e., >2%), multiple imputation methods will be used.

## **E. Statistical Analysis**

### **E.1. Evaluation of randomization, balance, and attrition**

We will test for balance between treatment and control based upon observable baseline characteristics for the overall study population.

Because differential attrition correlated with treatment could introduce bias into our results, we will also evaluate the attrition rate and assess for balance between treatment and control based upon both baseline characteristics for the final analytic sample (and attriters) and potential causes of attrition.

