### **D.2. Planned Outcomes**

#### **Primary Outcomes:**

Primary outcomes are measured as event counts between baseline and 18 months after the beginning of study interventions using OCFS administrative data. We will treat all primary outcome events as integer count variables, with the exception of preventive services which will be treated as binary (services delivered / no services delivered). In the event that observed study outcomes are rare in the sample, we will treat primary outcomes as binary (occurred / did not occur) instead of treating rare outcomes as event counts.

The primary study outcomes (and variable class) are:

- Investigative Track OCFS maltreatment cases: event count
- Family Assessment Response (FAR) track OCFS cases: event count
- Total OCFS cases: event count as sum of investigative track and FAR track cases
- Indicated OCFS maltreatment investigations: event count
- Substantiated OCFS maltreatment investigations: event count
- OCFS foster care placements: event count
- Preventive services for families at risk of foster care: binary

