#### E.4. Alternative specifications and sensitivity analyses

We evaluate the sensitivity of all analyses to the specification of informative priors derived from prior studies of the impacts of guaranteed income in a Bayesian framework by estimating all models specified above using MCMC. Prior parameter distributions will be specified within conservative bounds based on established empirical research.

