#### E.5. Statistical significance and adjustments for multiple comparisons

Statistical significance was defined as two-sided  $P < 0.05$  for the primary outcome. We will use the Benjamini-Hochberg or similar procedures to calculate adjusted p-values that account for testing of multiple outcomes.

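### The plan names differential attrition as a source of bias but prespecifies only diagnostics; the survey outcomes have no missing-outcome method, although linked agency records could reduce the bias

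*Combined protocol and SAP*

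**What the plan says.** E.1 gives the reason for looking at dropout: "Because differential attrition correlated with treatment could introduce bias into our results, we will also evaluate the attrition rate". It then plans to "assess for balance between treatment and control based upon both baseline characteristics for the final analytic sample (and attriters) and potential causes of attrition". It does not define the analytic sample and does not say what happens if imbalance is found.

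E.2 takes an intent-to-treat approach that "compares outcomes for those randomized into the treatment group to those who were randomized into the control group". It fits one general model with random intercepts for individual, period and county, treatment-by-period terms, and demographic covariates.

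Two other sections could have supplied a missing-outcome method. D.3 opens its imputation rule with "In the event that there are high levels of missingness for any key covariate", so it covers covariates only. E.4 reads "We evaluate the sensitivity of all analyses to the specification of informative priors", and nothing in it concerns missing data.

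The two outcome families have different sources. For the primary outcomes, D.2 says: "Primary outcomes are measured as event counts between baseline and 18 months after the beginning of study interventions using OCFS administrative data". The secondary outcomes come from surveys at baseline, 6, 12 and 18 months.

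**The concern.** One arm receives $500 a month. The other receives no transfer and can only join compensated research activities. Higher survey loss among controls is foreseeable, and E.1 anticipates it.

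The difficult case is dropout driven by something after baseline. A family with a new OCFS case may stop answering a study run with the same agency. If this happens more among controls, the remaining controls look better off than the randomised control group. On a distress-type score the treated-minus-control difference is then pushed upwards, so a benefit of cash is understated. Baseline balance can look acceptable throughout.

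E.2's model cannot see this mechanism, because agency events are not among its covariates. The trial nevertheless links those events to its participants.

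**Working it through.** **Inputs from the documents.** Allocation (D.1): "We will randomly select 50 households per county into the treatment arm, and 100 households per county into the control arm", so 3 × 50 = 150 and 3 × 100 = 300. Significance is two-sided at 0.05 (E.5). The documents give no expected attrition, event rate, SD, effect size or power, so there is no figure of the plan's own to reproduce. Every rate below is an assumption, and the true treatment effect is set to zero.

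**1. Closed form over three follow-up waves.** Assume a 9% new-case risk per wave. Control dropout is 50% at a wave with a new case and 10% otherwise; treated dropout is 5.3% regardless.
- Control loss per wave: 0.09 × 0.50 + 0.91 × 0.10 = 0.136. By 18 months: 1 − 0.864³ = 0.355.
- Treated loss by 18 months: 1 − 0.947³ = 0.151.
- Ever a new case, all families: 1 − 0.91³ = 0.246.
- Per-wave case share among control stayers: 0.045 / 0.864 = 0.052. Ever a new case among control stayers: 1 − 0.948³ = 0.148.
- Gap between arms among stayers: 0.246 − 0.148 = 0.098.
- Bias = gap × lasting shift in outcome after a case. For shifts of 0.5 to 0.8 SD: 0.098 × 0.5 = 0.049 and 0.098 × 0.8 = 0.078 SD.

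**2. Planned type of model.** A four-wave random-intercept model with wave-by-treatment effects was simulated under these assumptions (150/300, 1,000 runs). The 18-month estimate was biased by 0.046 to 0.075 SD and rejected in 8% to 13% of runs, against about 6% to 7% with complete data. Using all waves therefore removes little of the closed-form bias when dropout coincides with the case. A further check of this type of model over other assumed rates gave about 0.03 to 0.09 SD.

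**3. Sensitivity to the mechanism.** In a single-wave version, 25% of families have a new case. Control dropout is 60% after a case and 25% otherwise, which is 0.25 × 0.60 + 0.75 × 0.25 = 34% overall.
- Case share among control stayers: 0.100 / 0.6625 = 0.151; gap 0.25 − 0.151 = 0.099. Simulated bias of baseline-adjusted complete-case analysis: 0.056 / 1.02 = 0.055 SD, with 9% rejection.
- A separate simulation compared that analysis with the random-intercept model. Bias was 0.061 and 0.062 respectively when dropout coincides with the case, and 0.058 and 0.045 when it comes one wave later.
- If treated families also leave after a case (35% against 12%), the treated-stayer share is 0.1625 / 0.8225 = 0.198 and the gap falls to 0.047. Simulated bias of the baseline-adjusted analysis: 0.029, with 5.7% rejection.
- If control dropout after a case is 40%, the control-stayer share is 0.150 / 0.7125 = 0.211 and the gap is 0.039. Simulated bias: 0.026, with 6.4% rejection.

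**4. What agency data add.** Simulation with about 15% against 30% attrition, 3,000 runs, bias in SD units:

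| Dropout depends on | Raw stayers | Baseline-adjusted | Weighted with agency events |
|---|---|---|---|
| Baseline score | 0.086 | −0.001 | −0.001 |
| Agency events | 0.047 | 0.035 | 0.002 |
| The unseen outcome | 0.170 | 0.129 | 0.124 |

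Imputation with the new-case indicator, in the setting of step 3, likewise cut the bias to 0.002 SD.

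**5. Scale.** The detectable difference at 80% power is (1.960 + 0.842) × √(1/n₁ + 1/n₀). With 150 and 300 it is 0.280 SD. With 15% and 35% loss (127.5 and 195) it is 0.319 SD. A bias of 0.03 to 0.09 SD is 9% to 28% of 0.319.

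**The case against.** The strongest reply is that E.2 already contains a response. The repeated-measures model keeps partial responders and is valid when dropout depends on observed scores and covariates. That stands: the first row of the table shows baseline-driven dropout handled completely. E.1's checks also reach beyond baseline characteristics to possible causes of attrition, which could include a new case. But that phrase is vague and no correction follows from it, and the model does not contain the agency events.

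The size also depends on a chosen mechanism. Symmetric or milder case-driven dropout roughly halves the bias, and the near-zero result after adjustment is expected when the adjustment contains the true driver of dropout. Both points stand.

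Three stronger readings are tempting but unsupported.
- A reader might infer that survey attriters leave the primary analysis. With 15% against 25% to 35% attrition and attriters at 1.5 to 2 times the case rate, that would give null rate ratios from 1.125 / 1.075 = 1.05 to 1.35 / 1.15 = 1.17. But E.2 states intent-to-treat over those randomised, and D.1 and D.2 take primary outcomes from linked records with no survey-completion condition. The figures rest on an exclusion that the plan never states.
- A reader might infer that agency records cover every randomised family. D.1 describes linkage by name and date of birth and says nothing about completeness.
- A reader might infer that agency data would correct the survey results. They help only as far as they explain the dropout, as the last row of the table shows.

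**Conclusion.** The point holds for the survey outcomes, all of which are secondary. The plan identifies a bias, measures its symptoms and specifies no missing-outcome method or missing-data sensitivity analysis. Under assumed case-driven dropout concentrated in controls, the planned type of model keeps a null bias of about 0.03 to 0.09 SD at 18 months. The bias is smaller if treated families behave similarly, and essentially absent if dropout depends only on baseline scores. All attrition rates, case risks and associations are assumptions.

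For the primary outcomes the plan needs a clarifying sentence, not a changed analysis. The term for the analytic sample in E.1 is undefined and not limited to surveys, but E.2's intent-to-treat statement points to keeping everyone.

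**What to change.** **E.4, survey outcomes.** Add multiple imputation of missing outcomes, done separately by arm, using baseline and earlier scores and each family's agency events up to that wave. Inverse-probability weighting on the same variables is an alternative. Agency events should enter the imputation or weighting model only. They occur after randomisation and are themselves outcomes, so adding them to E.2's covariates could adjust away part of the treatment effect. Add a delta-shift tipping-point analysis, at least in the control arm, because agency data barely help if dropout depends on the unseen score itself.

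**E.1 and E.2, clarification.** State that the final analytic sample refers to survey outcomes, and that administrative primary outcomes are analysed in all randomised families that can be linked, whatever their survey status. Report linkage completeness by arm.

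**Cost.** SAP text and extra analysis, with no new participant contact. OCFS would have to supply event counts by survey wave as well as the baseline-to-18-month total, which the documents do not currently promise. One more sensitivity table is needed.
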